### 3.3 Sample Size Considerations

This study has been sized making the following assumptions:

- Inferential testing is at the (two-sided) 5% level, and with a desired power of 80%.
- The primary endpoint is the difference between treatment groups in change from baseline WOMAC Pain (average of 5 pain items) at 12 weeks post-dose, as measured using a 0-10 scale
- The standard deviation of the endpoint is 2.2, as assessed from review of similar studies from clinicaltrials.gov
- The desired difference to detect is 0.8.

Based on these assumptions, a sample size of approximately 120 subjects per treatment group is required. Assuming a drop-out rate of approximately 20%, 150 subjects will be randomized and dosed in each treatment arm.

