- Difference between treatment groups in SF-36 at Weeks 12 and 24
  - Each of the 8 SF-36 domains, as well as the two component scores (Mental and Physical), will be modeled separately using an ANCOVA model with treatment, site (possibly grouped; see Section 4.2), and covariate baseline score as covariates.
  - SF-36 scoring will be directly obtained from the QualityMetric PRO CoRE software.
- Difference between treatment groups in average rescue medication usage at Weeks 1-24
  - The weekly average frequency of rescue medication use will be based on the ePRO diary data. Rescue medication will be considered to be taken on each day where it is recorded that rescue medication was consumed for index knee pain. Weekly averages will be calculated based on actual days in the study. At least 4 non-missing rescue medication diary entries in a week must be available for the weekly average at that week to be calculated. Section 4.3 describes the imputation strategy for instances when less than 4 rescue medication entries are available at a given week. The weekly average frequency of rescue medication use will be analyzed at actual weeks with an ANCOVA model with site (possibly grouped; see Section 4.2), treatment, and baseline (pre-dose) weekly average frequency of rescue medication use as covariates.

Depending on the distribution of the observed data, the weekly average frequency of rescue medication use may be transformed appropriately prior to fitting the model.

- The average daily dosage (mg) of rescue medication will be based on information from the rescue medication accountability eCRF pages only. Average daily dosage (mg) of rescue medication will be calculated between each observed scheduled visit. This will be calculated by multiplying 500 mg by the number of tablets within a bottle consumed divided by the number of days between visits associated with the bottle. Note that at each visit, rescue medication is returned and accounted for from the previous observed visit and new medication is potentially both dispensed and re-dispensed. It will be assumed that rescue medication taken on the day of return/dispensing will be from the newly dispensed/re-dispensed medication. For a

	EP-104IAR-201 Statistical Analysis Plan	Version: Final 1.0
	Date: 14-Jun-2023	Page 23 of 38

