given observed visit, the number of days between visits will be calculated as: start date of current visit – start date of previous visit. If an interim visit is missing but dispensing and return information is provided at the previous and later visits, then rescue medication usage at the later visit will be calculated according to the period between the two observed visits. The number of tablets consumed will be calculated from the eCRF data as: number of tablets dispensed/re-dispensed – number of tablets in returned kit – number of tablets not accounted for. If a subject marks “unknown” for number of not accounted for tablets, then the number of consumed tablets cannot be calculated and, therefore, the average daily dose of rescue medication for that period will be considered missing. Rescue medication may be calculated for following visits if all dispensing and return information is provided for those periods. If no medication is dispensed at a given visit, then no medication is assumed to have been taken between that visit and the next or until new rescue medication is dispensed, if any. If this occurs, then the daily average dosage (mg) will be considered 0 while the subject is in the study.

The average daily dosage (mg) will be analyzed at each post-baseline scheduled visit with an ANCOVA model with site (possibly grouped; see Section 4.2, treatment, and baseline average daily dosage (mg) as covariates.

- Difference between treatment groups in average activity levels at Weeks 1-24
  - This analysis will be analogous to the average rescue medication endpoint above.
  - Average daily activity level will be transformed to a 0-1 scale, where 0=Low, 0.5=Moderate and 1=High.
- Difference between treatment groups in WOMAC Pain responder categories at Week 4, Week 8, Week 12, Week 18, and Week 24
  - Subjects will be considered to be an X% responder if they have at least an X% decrease from baseline WOMAC Pain.
  - Separate summaries for 30% response, 50% response and 70% response will be presented. Each summary will be done by time point and treatment, and will include the number of subjects with data, the number and percentage of responders as well as the P-value from Fisher’s exact test comparing proportions of responders between treatment and vehicle.

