## 4.3 Missing Data

Handling of missing data for assessing the primary and secondary endpoints is discussed in Sections 3.7, 3.8 and 4.5. Handling of plasma/serum values that are BLQ with respect to the pharmacokinetic analyses are described in Section 3.9. Additional considerations include:

- For the derivation of duration of symptoms in the index knee (years) and time since diagnosis in the index knee (years), partial dates will be imputed with the following rules:
  - When only the year is available (both month and day are missing), then the month will be imputed as July and the day will be imputed as 1.
  - When the month and year are available (only day is missing), then the day will be imputed as 15.
  - When only the year is available and it is the same year as administration of study drug, the duration in days will be calculated as the day of the year study drug was administered divided by two.
- Intermittent missing ePRO-collected diary data for rescue medication, activity levels and daily pain (NPRS) for post-baseline weeks will be imputed in instances when less than 4 entries are available at a given week. Last observation carried forward (LOCF) will be applied to carry forward the most recent post-baseline diary entries so that 4 entries are made available at a week. For example, if a subject has only 1 entry at a given week, the 3 most recent entries from previous post-baseline weeks will be carried forward to compute a weekly average out of 4 days. Similarly, if a subject has only 3 entries at a given week, only the 1 most recent entry from previous weeks will be carried forward to compute a weekly average out of 4 days.
- For the SF-36 survey, PRO CoRE will be used to impute missing values via proration, whereby the missing responses will be replaced with the mean of the observed scores of the completed questions within the same scale (per subject and timepoint). PRO CoRE will only be used in instances where at least  $\frac{1}{2}$  items in each of the eight scales are non-missing. If less than  $\frac{1}{2}$  items are completed within a scale or the complete scale or survey is missing, no imputation will be applied.

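### Per-time-point ANCOVAs for rescue use, rescue dose, activity and SF-36 drop leavers from later comparisons; the SAP's own repeated-measures model would use their data

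*SAP*

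**What the plan says.** SAP 3.8.2 sets out two kinds of model for the additional secondary endpoints.

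- **Repeated-measures model.** WOMAC, NPRS, PtGA and MDGA scores are analysed as for the primary endpoint. That is the MMRM of SAP 3.7, which the SAP justifies under missing at random (MAR).
- **ANCOVA at each time point.** For rescue frequency: "The weekly average frequency of rescue medication use will be analyzed at actual weeks with an ANCOVA model with site", treatment and baseline frequency. For rescue dose: "The average daily dosage (mg) will be analyzed at each post-baseline scheduled visit with an ANCOVA model". Activity level is to be handled analogously to rescue use. The eight SF-36 domains and two component scores "will be modeled separately using an ANCOVA model", at Weeks 12 and 24.

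The missing-data rules for the second group are narrow.

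- **Diary data (SAP 4.3):** "Intermittent missing ePRO-collected diary data for rescue medication, activity levels and daily pain (NPRS) for post-baseline weeks will be imputed" when a week has fewer than four entries, by carrying recent entries forward until there are four. Both worked examples are weeks with at least one entry.
- **SF-36 (SAP 4.3):** items are prorated within a scale. Nothing is imputed when a whole scale or survey is missing.
- **Rescue dose (SAP 3.8.2):** the zero rule applies only while the subject is in the study.
- **Early-exit visits (SAP 4.4):** these count as unscheduled and are kept out of the analyses, although Protocol 9.2.5.7 and 9.2.6 collect SF-36 and rescue counts at that visit.

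On the number leaving, SAP 3.3 says: "Assuming a drop-out rate of approximately 20" per cent. The protocol synopsis makes clear that this is over the course of the study.

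**The concern.** These four measures are collected repeatedly on the same subjects, but the ANCOVAs have no time term and no subject effect. A leaver's earlier post-dose values therefore cannot inform a later week. An observed-case ANCOVA needs leaving to be unrelated to earlier post-dose values, given treatment, site and baseline. That is a stronger assumption than the MAR assumption made for pain.

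The SAP treats leaving as possibly informative elsewhere. Its sensitivity analysis of the primary endpoint imputes lack-of-efficacy leavers as if on placebo (SAP 3.7), and subjects who discontinue before Week 12 count as strict non-responders (SAP 3.8.1). Rescue use is closely tied to poor pain control, yet it gets neither safeguard nor the MAR model. At Week 24, pain would be estimated using everyone's data and rescue use from stayers only, although a reader will set the two side by side to judge whether analgesic use explains a pain result.

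**Working it through.** **The plan's own figures.** Inputs from SAP 3.3: "Inferential testing is at the (two-sided) 5% level, and with a desired power of 80" per cent; "The desired difference to detect is 0.8"; "The standard deviation of the endpoint is 2.2, as assessed from review of similar studies from clinicaltrials.gov".

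- n per arm = 2 × (1.960 + 0.842)² × 2.2² / 0.8² = 2 × 7.85 × 4.84 / 0.64 ≈ 119, against a stated figure of about 120. Power at 120 per arm is 80.4%.
- 120 / (1 − 0.20) = 150 per arm, as stated.

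The sizing reproduces, but it is for WOMAC Pain. The documents give no effect, SD or correlation for rescue use, activity or SF-36.

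**Loss of precision alone.** If 240 of 300 remain at Week 24, the standard error grows by √(300/240) = 1.118, about 12%, before any bias. Earlier weeks lose less because the 20% is cumulative.

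**Bias, two post-dose time points.** Assumptions not in the documents: a standardised outcome with higher meaning worse; a true difference of 0.8/2.2 = 0.36 SD at both times; a baseline-to-outcome correlation of 0.4; an earlier-to-later correlation of 0.5, 0.7 or 0.85; and 20% leaving overall according to the earlier score. The simulation had 400,000 subjects per arm. Entries are the share of the true difference recovered at the later time, as a range over the three correlations. The last column carries the earlier score forward for leavers.

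| Leaving pattern | Leaving, EP-104IAR / vehicle | Observed-case ANCOVA | Model using earlier values | LOCF for leavers |
|---|---|---|---|---|
| Random | 20% / 20% | 1.00–1.01 | 1.00–1.01 | 1.00–1.01 |
| Worst 20% of each arm | 20% / 20% | 1.00–1.01 | 1.00–1.01 | 1.00 |
| Same rule in both arms, log-odds slope 0.5 per SD | 19% / 21% | 0.99–1.00 | 1.01 | 1.01–1.02 |
| Same rule, slope 1 | 17% / 23% | 0.92–0.97 | 0.99–1.00 | 1.01–1.04 |
| Same rule, slope 2 | 16% / 24% | 0.83–0.92 | 1.00 | 1.02–1.07 |
| Worst 20% of the pooled sample | 15% / 25% | 0.70–0.85 | 1.00–1.01 | 1.04–1.12 |
| Worst 25% of EP-104IAR, worst 15% of vehicle | 25% / 15% | 1.16–1.30 | 1.00–1.01 | 0.89–0.96 |

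Random leaving gives 0.997–1.009, so simulation noise is about 0.01. Slope 2 multiplies the odds of leaving by e² ≈ 7.4 per SD, and the last two rows use hard cut-offs. I treat those three rows as extreme.

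**Bias, six time points, trial-sized.** The settings were 150 per arm, a true difference of −0.364 SD, baseline correlation 0.5, residual correlation 0.5 + 0.5 × 0.6^lag, 14–20% gone by the last assessment, and 400 replicates.

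- Exit depending on the previous score: ANCOVA −0.325, a loss of (0.364 − 0.325)/0.364 = 10.7%; repeated-measures fit −0.356.
- Weaker dependence: ANCOVA −0.351 (3.6% loss); repeated-measures fit −0.360.
- Two time points as for SF-36, with 10–15% leaving after Week 12: ANCOVA −0.337 (7.4% loss); repeated-measures fit −0.357.

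A further six-point set, again with assumed correlations and exit model, varied the exit pattern by arm.

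- Common exit rule: ANCOVA −0.357 to −0.323, a loss of 2% to 11%.
- Equal exit rates: −0.363, no material bias.
- More exits on EP-104IAR: −0.389, an inflation of 0.389/0.364 − 1 = 7%.
- The repeated-measures fit stayed between −0.362 and −0.376 throughout, under both the true covariance and the compound-symmetry fallback of SAP 3.7.

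**The case against.** A baseline-adjusted ANCOVA at each visit is a conventional choice for supportive endpoints, and the shift is small beside the noise. With 120 per arm and a baseline correlation of 0.5, the standard error is about √(2/120) × √(1 − 0.25) = 0.112 SD. The 10.7% loss is 0.039 SD, roughly a third of that. The single-dose design also limits informative exit: Protocol 5.4 prefers that subjects stay, 8.1 keeps users of prohibited therapy in follow-up, and 7.5 allows rescue medication throughout. All of this stands and limits the weight of the point.

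It can also be said that SAP 4.3 does score leavers. SAP 3.8.2 refers to 4.3 for any week with fewer than four rescue entries, and a week with none literally qualifies. Limiting the rule to intermittent gaps points the other way, but no sentence settles it. A reader might infer that the SAP has no rule at all for the diary endpoints, and the documents do not support that. They support the natural reading plus an unresolved ambiguity. The ambiguity matters, because LOCF for leavers errs in the opposite direction to the observed-case ANCOVA in every biased row of the table.

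Finally, weekly rescue frequency is bounded, so a normal repeated-measures model is an approximation. That is true, but it applies equally to the ANCOVA, and the SAP already allows a transformation.

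**Conclusion.** The four endpoints have a weaker missing-data treatment than the other repeated measures in the same SAP section. The observed-case ANCOVA is biased when leaving depends on earlier post-dose values and differs by arm. Under plausible exit rules the bias is roughly 0–11% of the effect; it reaches 15–30% only under hard cut-offs with unequal exit. These sizes rest on assumed correlations, an assumed exit model and an effect size borrowed from WOMAC Pain.

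A reader might infer that the difference shrinks whenever the worse subjects leave. That does not follow. Equal shares of the worst leaving each arm give essentially no bias, and more of the worst leaving EP-104IAR inflates the difference. The documents give no drop-out rate by arm, so the direction cannot be predicted. Nor is 20% absent at every week: that figure is an assumed total to Week 24.

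The endpoints sit outside the testing hierarchy, so primary and key secondary conclusions do not change. This is a cheap improvement, not a flaw in the trial's main inference.

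**What to change.** In SAP 3.8.2, analyse rescue frequency, rescue dose, activity level and each SF-36 score with the repeated-measures model already specified for PtGA and MDGA.

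- Include treatment-by-time, pooled site and the endpoint's own baseline, with the same covariance fallback as SAP 3.7.
- Apply any transformation of rescue frequency before fitting.
- Report the contrasts at the same protocol weeks or visits. Averaging the diary over longer blocks is not needed: the endpoints are defined for Weeks 1–24 and the fallback covers non-convergence.
- State in SAP 4.3 that the LOCF rule does not extend past discontinuation.
- Keep the per-time-point ANCOVA as a sensitivity analysis.

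The cost is SAP wording and reuse of existing model code, with no new data. The downside is a little more modelling work, and reliance on MAR and approximate normality for a bounded diary measure.

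### The pill-count rescue dose (mg/day) can be a false 0 when earlier tablets were not counted, and too low when a bottle was collected between scheduled visits

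*SAP*

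**What the plan says.** SAP 3.8.2 measures rescue use in two ways: a weekly frequency from the diary, and an average daily dosage in mg from the accountability eCRF pages only. For the second measure it says:

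- Interval: "Average daily dosage (mg) of rescue medication will be calculated between each observed scheduled visit".
- Formula: 500 mg times the "number of tablets within a bottle consumed divided by the number of days between visits associated with the bottle". Tablets consumed are those dispensed or re-dispensed, minus those returned, minus those not accounted for.
- Premise: at each visit, "rescue medication is returned and accounted for from the previous observed visit and new medication is potentially both dispensed and re-dispensed".
- Unknown count of unaccounted tablets: "the average daily dose of rescue medication for that period will be considered missing". After that, "Rescue medication may be calculated for following visits if all dispensing and return information is provided for those periods".
- Missed visit: "If an interim visit is missing but dispensing and return information is provided at the previous and later visits", use is spread over the time between the two observed visits.
- Zero rule: "If no medication is dispensed at a given visit, then no medication is assumed to have been taken between that visit and the next"; a later dispensing, where there is one, ends this period. "If this occurs, then the daily average dosage (mg) will be considered 0 while the subject is in the study".

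On unscheduled visits, Protocol 9.2.7 lists the need for more rescue medication between visits as a circumstance for one. SAP 3.1 keeps unscheduled assessments out of the analyses except for baseline, ACTH tests and PK parameters. SAP 4.4 does the same for unscheduled data, with baseline and ACTH as its exceptions. Rescue accountability is in neither list.

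**The concern.** The zero rule is triggered by the absence of dispensing alone. It does not require that earlier tablets were returned and counted. Under Protocol 9.2.5 sites top up supplies at a visit only where needed, so a visit without dispensing is ordinary, and one reason for it is that the subject still has tablets. If those tablets were not brought in, they can be taken in the following interval while the dose is recorded as 0. The clause about the next dispensing ends the zero period but does not deal with tablets already at home.

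The second gap concerns extra bottles. If a bottle issued at an unscheduled visit is left out, the dose is understated for subjects who needed more than their scheduled supply, so the error falls mainly on heavier users.

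What is at stake is limited but specific. Subjects do not record tablets per day (Protocol 9.1.7.5), so the pill count is the only analysed measure of how much acetaminophen was taken. The diary gives frequency only.

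**Working it through.** The plan states no figure for this endpoint, so there is none to reproduce.

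**Inputs.** Tablets are 500 mg with a cap of 3,000 mg/day (Protocol 7.5), which is 3,000 / 500 = 6 tablets a day. Visits 6, 7 and 8 fall on Days 57, 85 and 127 (Protocol 9.2.5.4 to 9.2.5.6), giving intervals of 28 and 42 days. Bottle size is not given; 100 tablets is assumed, with 50 as an alternative. Formula: mg/day = 500 × tablets consumed / days.

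**Zero rule.** Let 100 tablets go out at Visit 6. At Visit 7 the bottle is not brought and nothing is dispensed. At Visit 8, 30 tablets are returned.

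- Per-bottle formula, Days 57 to 127: 500 × (100 − 30) / 70 = 500 mg/day.
- Zero rule, Days 85 to 127: 0 mg/day.
- Unknown-count rule: the period to Visit 7 is missing if the site marks the unaccounted count as unknown.
- Missed-visit rule: had the subject skipped Visit 7 altogether, use would be spread over Days 57 to 127, again 500 mg/day. Attending without the bottle gives 0 for the second part of the same period.

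The count cannot show how the 70 tablets were split around Day 85. The 0 is correct only if all 70 were taken before then. The SAP does not say which sentence prevails, so the same record can be scored as 0, as missing or as a real dose.

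Effect on an arm's mean at a true 500 mg/day: each 1% of the arm scored a false 0 lowers it by 0.01 × 500 = 5 mg/day; 5% lowers it by 25 mg/day.

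**Extra bottle left out.** Keeping the per-bottle formula, the understatement is 500 × (tablets taken from the extra bottle) / days.

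| Visit 7 to Visit 8 (42 days) | True | Extra bottle omitted | Understatement |
|---|---|---|---|
| 100 + 100 tablets, 150 used, first bottle emptied | 500 × 150 / 42 = 1,786 | 500 × 100 / 42 = 1,190 | 500 × 50 / 42 = 595 (33%) |
| 50 + 50 tablets, 80 used, first bottle emptied | 500 × 80 / 42 = 952 | 500 × 50 / 42 = 595 | 500 × 30 / 42 = 357 (38%) |

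Over a 28-day interval, 50 tablets from the extra bottle would be 500 × 50 / 28 = 893 mg/day.

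**Could a subject run out?** At the cap, 28 and 42 days need 6 × 28 = 168 and 6 × 42 = 252 tablets. One 100-tablet bottle lasts 100 / 6 = 16.7 days at the cap, and use above 1,190 mg/day empties it within 42 days. This assumes one bottle per interval, which the documents do not state.

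**The case against.** **Zero rule.** The section assumes that tablets come back at every visit, and Protocol 7.5 tells subjects to bring their bottles. Read in order, the sentences before the zero rule deal with incomplete counts, so the zero rule can be taken to apply only to complete ones. This shows the likely intention, and it means the rule is right in the ordinary case. A reader might infer that every visit without dispensing yields a wrong 0; the documents do not support that, because stock that is counted and handed back enters the formula as re-dispensed. But the zero-rule sentence states no such condition and mentions only dispensing, so the conflict remains where a bottle was not brought.

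**Extra bottle.** SAP 3.1 speaks of assessments, in the context of summaries by visit or time point, and issuing a bottle is hardly an assessment. A blanket exclusion would also drop adverse events and concomitant medications recorded at unscheduled visits, which cannot be intended. SAP 3.8.2 relies on the accountability pages without limiting which entries count. A programmer could therefore include the bottle. That is fair, but SAP 4.4 uses the wider term data and names its exceptions, so inclusion would rest on judgement against the literal text.

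**Larger or negative errors.** A reader might go further and subtract the extra bottle's leftovers while ignoring its issue. The first example would then give 500 × (100 − 50) / 42 = 595 mg/day (67% too low), and a subject with 80 of 200 tablets used would get 500 × (100 − 120) / 42 = −238 against a true 952. The per-bottle formula does not call for this. By bottle, that second subject scores the true 952 if all 80 came from the first bottle.

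**Importance.** Protocol 9.1.7.5 itself calls the pill-count average approximate, and Protocol 7.5 lets the tablets be used for other pain. Both points stand.

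**Conclusion.** The point holds in limited form and is minor. The zero rule can give a false 0 when earlier tablets were not returned and counted at the visit, and it then contradicts other sentences of SAP 3.8.2. Read literally, SAP 3.1 and 4.4 also understate the dose for a subject who collected an extra bottle, by at least what was taken from it. In the examples the errors are 500 mg/day for the affected interval and 357 to 595 mg/day over 42 days.

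These sizes rest on assumed bottle sizes and, for the extra bottle, on the first bottle being emptied. The frequency of either case is unknown.

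A reader might also infer a biased treatment comparison. The documents give no basis for that: imbalance between arms is not documented, and if the errors are equal in both arms the expected difference is unchanged. The primary and key secondary analyses and the diary frequency measure are unaffected, and all data are listed.

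**What to change.** In SAP 3.8.2:

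1. Assign 0 mg only when all prior stock was returned and counted and nothing was dispensed or re-dispensed.
2. Otherwise compute the dose over the combined interval to the next complete count, or set the interval to missing. Say which applies when.
3. Include tablets dispensed or returned at unscheduled visits in the enclosing scheduled interval, as a stated exception to SAP 3.1 and 4.4. SAP 4.4 classes early exit visits as unscheduled, so the exception should name them too.

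As a clarification, list the visits that bound the intervals, since Visit 3 has no rescue count (Protocol 9.2.5.1).

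The cost is two or three sentences and a small programming change, using accountability data already collected. The downside is that a few intervals become longer or missing.
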